## **1. Background**

Treatment of osteosarcoma has evolved in the last 40 years: with the introduction of neo-adjuvant chemotherapy, 5-year survival rates for patients affected by high-grade osteosarcoma have improved from 15% to more than 70%.

To date, many osteosarcomas are cured by multiagent chemotherapy and surgery, but a significant number still relapse: after treatment of the primary osteosarcoma, 40% to 50% of patients will develop local relapse (LR), distant metastases (DM) or both.

Few analyses in literature report on locally recurrent disease as it remains uncommon, with LR rate ranging from 4% to 10%. Prognosis of patients experiencing LR is generally considered poor, however most data available do not provide sufficient details. DM are such an overriding determinant of survival, and LR is so infrequent, that it is difficult to study local recurrence as an independent variable.

Also, in case of LR, while the importance of achieving a second surgical complete remission is well known (CR2), the role of second line chemotherapy is under discussion, with a mono-institutional experience showing no advantage in of chemotherapy after local relapse. Several molecules and their receptors are known to be involved in migration and invasiveness of tumour cells including CXCL12 (SDF-1) which is the ligand of Receptor-4 (CXCR4). The binding of CXCL12 to CXCR4 it is known to activate downstream cascades involving many signalling pathways, such as JAK/STAT, PI3K/Akt, MAPK, JNK which are key in cell migration. The expression of CXCR4 is low or absent in normal cells, while it is elevated in tumor cells. There are preclinical evidences that CXCR4 has an important role on tumor progression in sarcoma. Also, nuclear expression of CXCR4 and IGF-1R negatively influences survival in patients with localized soft tissue sarcoma.

## **2. Objectives**

Aim of this study is to analyse the modalities of diagnosis (symptoms versus planned radiology) of LR for high-grade osteosarcoma patients, pattern of recurrence, treatment of LR and factors influencing post-LR survival (PLRS) on the role of second line chemotherapy, margins, Local relapse-free interval (LRFI) (“early LR” recurrences with an LRFI ranging between 1 and 24 months, and “late LR” as those having an LRFI longer than 24 months).

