### **Secondary Objectives**

- analyse the modalities of diagnosis of LR in high-grade osteosarcoma
- pattern of recurrence
- treatment of LR
- Prognostic factors for PLRS (second line chemotherapy, surgical margins, surgical complete remission after LR (CR2), type of surgery)

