#### **4.1 Study population**

We plan to include approximately 50 patients in 36 months.

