##### **Inclusion criteria**

- Patients who experienced LR as first event of recurrence after treatment for localized high-grade osteosarcoma of bone, including cases with synchronous lung metastases
- Adequate patient compliance to follow-up visits
- Written informed consent prior to any study-specific analysis and/or data collection
- No age limits

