## 5.1 Study population

Through the collaboration of the joining institutions, we plan to include approximately 100 patients

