## 6. Statistics

To the case series will be applied a descriptive statistic.

For the exploratory objectives, positive and negative expression of CXCR4 and CXCL12 (nuclear and cytoplasmatic) will be correlated with ES and OS.

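### The local relapse-free interval is named as a factor for PLRS but given only as a split at 24 months, has no class below 1 month, and is missing from the secondary-objective factor list

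*Protocol*

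**What the plan says.** Protocol section 2 (Objectives) sets out to study "factors influencing post-LR survival (PLRS) on the role of second line chemotherapy, margins, Local relapse-free interval (LRFI"). In the same sentence it defines early local relapses as "recurrences with an LRFI ranging between 1 and 24 months" and late ones "as those having an LRFI longer than 24 months". No other form of LRFI appears in the protocol.

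The Secondary Objectives restate the factors as "Prognostic factors for PLRS (second line chemotherapy, surgical margins, surgical complete remission after LR (CR2), type of surgery"). LRFI is not among them.

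Prospective eligibility (section 4.1) rests on "Patients who experienced LR as first event of recurrence after treatment for localized high-grade osteosarcoma of bone". Neither section 4.1 nor section 5.1 sets a minimum interval to relapse. The planned sizes are about 50 prospective patients ("We plan to include approximately 50 patients in 36 months") and about 100 retrospective ("we plan to include approximately 100 patients"). For the main analysis, section 6 says only: "To the case series will be applied a descriptive statistic".

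**The concern.** Three faults meet on one factor.

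- **Form.** The split treats relapses at 2 and 23 months as alike, and relapses at 23 and 25 months as opposites. In a series of about 150 patients with an uncommon event, that is a costly way to examine a factor the study singles out.
- **Coverage.** The early class starts at 1 month, so an eligible patient who relapses sooner belongs to neither class. If the floor is meant to separate persistent disease from relapse, the protocol does not say so.
- **Consistency.** The aim and the secondary objective give different factor lists. A reader cannot tell whether LRFI is a planned factor. About two thirds of the patients are retrospective, so outcomes may already be known when that choice is made.

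Behind these lies a practical question: when does the interval start, and will both cohorts record that date?

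**Working it through.** The protocol gives no effect size, death count or power for LRFI, so there is no figure of its own to reproduce.

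**1. The two factor lists (both in section 2)**

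| Factor | Aim | Secondary Objectives |
|---|---|---|
| Second-line chemotherapy | yes | yes |
| Surgical margins | yes | yes |
| LRFI | yes, with classes | no |
| CR2 | no | yes |
| Type of surgery | no | yes |

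**2. Coverage of the classes.** Early is 1 to 24 months and late is over 24 months. An interval under 1 month is in neither, and no eligibility criterion removes it. The documents do not give the share of such patients. If it is 0% to 2%, then 150 × 0 = 0 to 150 × 0.02 = 3 patients have no class.

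**3. Information kept by a two-class split.** Assume that log LRFI is normal and acts linearly on the log hazard. With a share q in the early class, the split keeps φ(z_q)² / [q(1 − q)] of the information in the continuous variable. Here z_q is the normal quantile of q and φ is the normal density. The protocol does not give q, so a range is shown. Planned N = 50 + 100 = 150.

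| q (assumed) | Kept | Lost | 150 × kept |
|---|---|---|---|
| 0.5 | 0.637 | 36% | 95 |
| 0.6 | 0.622 | 38% | 93 |
| 0.7 | 0.576 | 42% | 86 |
| 0.8 | 0.490 | 51% | 73 |
| 0.9 | 0.342 | 66% | 51 |

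For example, at q = 0.8, z = 0.842 and φ(z) = 0.280, so 0.280² / (0.8 × 0.2) = 0.49.

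**4. The same loss as power.** Approximate power is Φ(√(d × kept) × |log HR| − 1.96), where d is the number of deaths and HR is per standard deviation of log LRFI. Neither is in the protocol. HR is taken as 0.75, so |log HR| = 0.288.

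| Deaths (assumed) | Continuous | Split, q = 0.5 | Split, q = 0.8 |
|---|---|---|---|
| 75 | 70% | 51% | 41% |
| 90 | 78% | 59% | 48% |
| 105 | 84% | 65% | 54% |

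For 90 deaths, the continuous form gives √90 × 0.288 − 1.96 = 0.77, so power is 78%. The split at q = 0.8 gives √(90 × 0.49) × 0.288 − 1.96 = −0.05, so power is 48%.

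**5. Dates needed.** The protocol does not say whether LRFI runs from diagnosis, surgery or end of treatment. The retrospective list (section 5) includes the dates of surgery and of local relapse. The prospective list (section 4) includes the recurrence date and, it appears, the date of diagnosis. For the primary tumour it names surgery without a date. As listed, LRFI from surgery can be derived in the retrospective cohort but not clearly in the prospective one.

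**The case against.** The strongest reply is that the protocol defines two labels and nowhere says LRFI will be analysed only through them. Section 6 is descriptive, and an analysis plan not shown may set another form. That stands in part, and it is why the loss is stated conditionally. Still, the protocol itself chose the cut and gives no other form, so the choice is open to comment.

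The size of the loss is entirely assumed, and that also stands. With a real threshold near 24 months, the split could lose little or nothing. Patient equivalents are only a guide, because information on a survival factor depends on deaths.

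The gap below 1 month probably affects few patients. The two factor lists can also be read as complementary, since the secondary list adds CR2 and type of surgery. Neither reply says which list governs, or where an early relapse would be placed.

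A reader might go further and infer three things that the documents do not support:

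- *Chemotherapy or margin comparisons will carry residual confounding from a coarse LRFI.* No adjusted comparison is planned in the protocol.
- *Patients under 1 month will be dropped.* Nothing says so. Eligibility does not depend on the early or late label.
- *Omitting LRFI from the secondary list loses data.* It does not. It leaves the status of the factor unclear.

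**Conclusion.** The point holds in a limited form. Three faults can be read directly from section 2 and the eligibility criteria: LRFI is given only as a split at 24 months, the classes leave out eligible patients under 1 month, and the secondary list omits a factor that the aim names. The interval also has no stated start date.

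The numerical cost is conditional. If the split is the only way LRFI is related to PLRS, about 36% to 51% of its information is lost. This requires normal log LRFI, a linear effect on the log hazard and 50% to 80% of patients in the early class. A more uneven split would lose more, and a true threshold near 24 months would lose less. The gap below 1 month is a definition fault, likely to touch 0 to 3 patients on an assumed share of up to 2%. None of this invalidates the study. It is worth correcting because the remedy is cheap.

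**What to change.** - Relate LRFI to PLRS as a continuous variable in log months, with a check for non-linearity that would also show a threshold if there is one. Keep early and late at 24 months for description.
- Make the classes exhaustive by defining early as 24 months or less, or state how intervals under 1 month are handled and why.
- Add LRFI to the prognostic factors in the Secondary Objectives so that the list agrees with the aim.
- State the date from which LRFI is counted, use it in both cohorts, and make sure the prospective CRF records it.

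The cost is a few lines of text, some extra analysis and one date field in the prospective CRF.

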### **Primary Objective**

- post-LR survival (PLRS)

### **Secondary Objectives**

- analyse the modalities of diagnosis of LR in high-grade osteosarcoma
- pattern of recurrence
- treatment of LR
- Prognostic factors for PLRS (second line chemotherapy, surgical margins, surgical complete remission after LR (CR2), type of surgery)

### **Exploratory Objectives**

Assessment of CXCR4 and CXCL12 (SDF-1) expression classified as nuclear, cytoplasmatic, and both in primary tumor, LR and DM

- Comparison of CXCR4 and CXCL12 (SDF-1) expression in the LR samples between the groups of patients with isolated LR and those presenting with LR and DM
- Comparison of CXCR4 and CXCL12 (SDF-1) expression on primary tumor in 3 group of patients:
  - 1- patients with non LR, nor DM (archival series from Rizzoli database)
  - 2- patients with isolated LR
  - 3- patients with LR + DM

## **3. STUDY DESIGN**

This is a multicenter retrospective and prospective study that will analyze all cases with of

diagnosis of LR in high-grade osteosarcoma from 01 January 1980 and all new cases referring to each participant site.

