#### **4. Prospective observational analysis and data collection**

Clinical data will be retrieved by patient charts.

A protocol-specific CRF reporting the results of the review will be provided.

Data from all patients diagnosed with OS will be prospectively entered in this platform.

Each patient will be provided with an informational leaflet for his/her general practitioner and asked to sign an informed consent prior to data entry.

The following information will be recorded in the database:

- Demographics – patient name, DOB, gender, date of first consultation, data of diagnosis
- Data on primary tumor – size, site, evidence of multifocality
- Data on histological diagnosis – morphology (classical type, proximal type, mixed), mitotic count, depth
- Data on staging at diagnosis – evidence of lymph-nodal and/or distant metastases
- Data on treatment of primary tumor – surgery, radiotherapy, chemotherapy
- Data on recurrence – type of recurrence, site, date
- Data on treatment of local relapse – surgery, radiotherapy, chemotherapy
- Data on treatment of metastatic disease – pulmonary metastasectomy, radiotherapy
- Data on chemotherapy for metastatic disease – line, regimen, number of cycles, best response, duration of response
- Patient status at last follow-up (dead of disease, DOD, alive with disease, AWD, nonevidence of disease, NED)

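### Prospective patients enter only after local relapse and consent, with no limit on the delay, so post-LR survival counted from relapse would be biased upward unless delayed entry is allowed for

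*Protocol*

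**What the plan says.** The primary objective in section 2 is post-LR survival. Its origin, event and censoring rule are not written out, but the name leaves the LR date as the only natural starting point.

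Entry to the prospective cohort is governed by these statements:

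- Section 3 takes "all new cases referring to each participant site" and sets no maximum interval from LR.
- The section 4.1 inclusion criteria admit "Patients who experienced LR as first event of recurrence after treatment for localized high-grade osteosarcoma of bone", so LR comes before eligibility. They also require "Written informed consent prior to any study-specific analysis and/or data collection" and "Adequate patient compliance to follow-up visits".
- Section 4 says each patient is "asked to sign an informed consent prior to data entry". Section 7 also makes consent a condition of inclusion.
- Section 4 further states: "Data from all patients diagnosed with OS will be prospectively entered in this platform". Read literally, this places entry at osteosarcoma diagnosis, before any LR, and does not fit the section 4.1 criterion.

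The section 4 data list includes the date of recurrence and, under demographics, the "date of first consultation". It has no consent date. Section 6 promises descriptive statistics and names no survival estimator.

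**The concern.** A survival time that starts at LR can be observed only in patients who live long enough to be referred and to consent. Deaths between LR and consent are invisible to the prospective cohort. Those who do enter bring with them an interval in which, by construction, they could not have died. If that interval is counted as time at risk, the denominator is inflated while the matching deaths are missing, and the error can only go upward.

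The affected quantity is the primary objective. The requirement for compliance with follow-up may add to the selection against patients who deteriorate early. The retrospective criteria in section 5.1 contain no consent or compliance item, and section 7, directly after the retrospective procedure, accepts that some eligible subjects may have died. The two cohorts therefore condition on survival differently, which matters if they are combined for PLRS.

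**Working it through.** The protocol gives no expected PLRS, no delay and no event count, so there is no figure of its own to reproduce. What follows shows the direction and plausible size of the bias.

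**From the protocol:** about 50 prospective patients (section 4.1) and about 100 retrospective patients (section 5.1).

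**Assumed:** exponential PLRS with true median m; a fixed delay d from LR to entry; a retrospective cohort free of this bias.

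**Formulas**

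- Share dying before entry: 1 − exp(−d ln2/m).
- True survival at 24 months: exp(−24 ln2/m).
- Naive prospective survival at 24 months, counted from LR among those alive at d: exp(−(24 − d) ln2/m).
- Naive prospective median: m + d.
- Pooled survival at 24 months: (50 × naive + 100 × true)/150.

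**Results for m = 24 (true 24-month PLRS 50.0%)**

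| Delay d (months) | Die before entry | Naive prospective 24-month PLRS | Naive prospective median (months) | Pooled 24-month PLRS | Pooled median (months) |
|---|---|---|---|---|---|
| 0 | 0.0% | 50.0% | 24.0 | 50.0% | 24.0 |
| 1 | 2.8% | 51.5% | 25.0 | 50.5% | 24.3 |
| 3 | 8.3% | 54.5% | 27.0 | 51.5% | 25.0 |
| 6 | 15.9% | 59.5% | 30.0 | 53.2% | 26.1 |

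For d = 3, for example: exp(−21 × 0.6931/24) = 54.5%, and (50 × 54.5 + 100 × 50.0)/150 = 51.5%.

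**Range over the assumed median, naive prospective 24-month PLRS**

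| m (months) | True | d = 1 | d = 3 | d = 6 |
|---|---|---|---|---|
| 12 | 25.0% | 26.5% | 29.7% | 35.4% |
| 24 | 50.0% | 51.5% | 54.5% | 59.5% |
| 36 | 63.0% | 64.2% | 66.7% | 70.7% |

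**Does delayed entry correct it?** Take m = 24 and delays that vary between patients, exponential with mean 3 months. The mean survival time is 24/ln2 = 34.6 months. Among patients who survive to entry, the mean delay is 1/(1/3 + 1/34.6) = 2.8 months and the mean time after entry is still 34.6 months. Dividing deaths by all time since LR gives a median of ln2 × (34.6 + 2.8) = 25.9 months. Counting time only from entry gives ln2 × 34.6 = 24.0 months, the true value. A simulation gave the same two figures. The correction uses each patient's own dates and needs no assumption about the length of the delay.

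**The case against.** The strongest reply is that no naive analysis has been specified. Section 6 fixes no estimator, and when a patient joins the risk set is something a SAP commonly settles. A reader might infer from the entry rule that PLRS is overstated as a matter of fact. The documents do not support that: it depends on the method and on the delay. The delay may be near zero where the participating site finds the LR during its own surveillance, and there is no truncation for a patient who consented before LR, as the all-patients sentence in section 4 would allow. This stands, and it limits the point to a conditional one. It does not remove it, because the entry rule without a time window, and the data list without a consent date, are fixed in the protocol itself.

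A reader might also infer that prospective patients, or treatments given at referral centres, will gain a false advantage. No objective compares the two cohorts or types of centre, and the retrospective series, drawn from institutional databases, may itself miss patients who died before reaching a site. That inference should not be drawn.

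Nor is the delay already on record. The first-consultation date is not tied to referral for LR and, for a patient treated at the site from diagnosis, comes before LR. It is not a safe entry time.

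On size, the standard error of a 50% survival estimate in 50 patients with complete follow-up is √(0.5 × 0.5/50) = 7.1 percentage points, larger than the 4.5-point bias at 3 months. That is true, but the bias has a known direction, does not shrink with more patients, and can be removed.

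**Conclusion.** The point holds in conditional form. Under section 4.1, prospective patients who consent after LR are left-truncated, and PLRS counted from LR without allowing for this would be biased upward. On the assumed 24-month exponential median, the bias at 2 years in the prospective cohort runs from nothing with no delay, through 1.5 points at 1 month and 4.5 at 3 months, to 9.5 at 6 months. Pooled with the retrospective patients, the last three fall to 0.5, 1.5 and 3.2 points. Both the median and the delay are assumptions. The pooled figures also take the retrospective cohort as unbiased and the numbers as 50 and 100. The point deserves correction because it touches the primary objective, and the entry date needed to handle it is not among the listed data items.

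**What to change.** 1. Define PLRS as running from the date of LR.
2. Add the consent (study entry) date to the CRF. Section 10 already requires the form to be personally dated, so the information exists at the site.
3. In the prospective cohort, let each patient join the risk set at the later of LR and consent. Patients who consented before LR are then at risk from LR.
4. Report the distribution of the LR-to-consent delay.
5. Reconcile section 4, which enters all osteosarcoma patients, with section 4.1, which requires LR, on the point of entry.

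The cost is one CRF field and a few sentences. With about 50 patients the early risk sets will be smaller, and the early part of the curve may be unstable. Delayed entry also assumes that entry time is independent of prognosis, which referral for further treatment could violate, so this should be stated as a limitation. If delays prove short, the estimates will barely change.

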#### **4. Prospective observational analysis and data collection**

Clinical data will be retrieved by patient charts.

A protocol-specific CRF reporting the results of the review will be provided.

Data from all patients diagnosed with OS will be prospectively entered in this platform.

Each patient will be provided with an informational leaflet for his/her general practitioner and asked to sign an informed consent prior to data entry.

The following information will be recorded in the database:

- Demographics – patient name, DOB, gender, date of first consultation, data of diagnosis
- Data on primary tumor – size, site, evidence of multifocality
- Data on histological diagnosis – morphology (classical type, proximal type, mixed), mitotic count, depth
- Data on staging at diagnosis – evidence of lymph-nodal and/or distant metastases
- Data on treatment of primary tumor – surgery, radiotherapy, chemotherapy
- Data on recurrence – type of recurrence, site, date
- Data on treatment of local relapse – surgery, radiotherapy, chemotherapy
- Data on treatment of metastatic disease – pulmonary metastasectomy, radiotherapy
- Data on chemotherapy for metastatic disease – line, regimen, number of cycles, best response, duration of response
- Patient status at last follow-up (dead of disease, DOD, alive with disease, AWD, nonevidence of disease, NED)

#### **Optional sub-study**

For both prospective and retrospective analysis, in all cases with formalin - fixed paraffin

embedded (FFPE) tissue available, and if funding might be secured, an immunohistochemistry analysis to assess the expression of CXCR4 and CXCL12 (SDF- in LR, DM and primary tumor) will be assessed both in the nucleus and cytoplasm, as described [10]. The optional exploratory revision will start only if funding might be secured.

#### **4.1 Study population**

We plan to include approximately 50 patients in 36 months.

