#### **5. Retrospective observational analysis and data collection**

Together with the prospective observational study, a retrospective analysis including all the cases with a histological diagnosis of localized high-grade osteosarcoma who experienced LR as first event of recurrence after treatment from 01 Jan 1980 to 31 Dec 2021 will be performed.

The data will be extracted retrospectively from prospectively maintained institutional database and will be checked through a revision of patient records.

The following data will be collected:

- demographics (gender, date of birth, age at diagnosis),

- disease characteristics (morphological subtype, dimension, primary site),
- treatment received (date of surgery, surgical margins, radiation therapy, timing of radiation therapy, chemotherapy, timing of chemotherapy, type of regimen used, best response according to RECIST 1.1)
- date of LR, modality of LR diagnosis, clinical suspect or imaging, presence, or absence of DM at LR diagnosis, type of treatment after LR, date of surgical complete remission after LR (CR2), surgical margins
- outcome (recurrence type and timing, patient status at last follow-up)

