## 7. Enrolment procedures

Patients considered eligible and who have provided a written informed consent will be

included into the study and their material will be used for the purpose of this research according to the protocol and to the informed consent provided.

For the retrospective analysis, the investigator will extract from Institute database the list of potential eligible patients for whom the tumor material is available. After the verification of the presence of the study enrollment criteria, the patient will be included in the study.

Due to the high incidence of mortality of the disease under investigation, it would be possible that some eligible subjects will be deceased

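### The prospective and retrospective targets imply local-relapse case rates that differ sevenfold without explanation, and Section 7 limits the retrospective list to patients with stored tumour tissue

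*Protocol*

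**What the plan says.** The Protocol describes one multicentre study with two parts.

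- **Prospective part (Section 4.1):** "We plan to include approximately 50 patients in 36 months". Eligibility is local relapse (LR) as first event after localized disease, with written consent and adequate compliance. LR found more than three months after metastatic disease is excluded. No limit is set on the date of the LR.
- **Retrospective part (Section 5):** "a retrospective analysis including all the cases with a histological diagnosis of localized high-grade osteosarcoma who experienced LR as first event of recurrence", with the period given as "after treatment from 01 Jan 1980 to 31 Dec 2021 will be performed". Section 5.1 adds: "Through the collaboration of the joining institutions", "we plan to include approximately 100 patients". The same three-month exclusion applies, and clinical information must be available. Tumour tissue is not among the criteria.
- **Enrolment (Section 7):** for the retrospective part, the investigator extracts from the institute's database "the list of potential eligible patients for whom the tumor material is available".
- **Tissue work (Optional sub-study in Section 4, and Section 11):** immunohistochemistry is done where tissue exists and only if funding is found.

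The primary objective is post-LR survival (PLRS). Section 6 specifies descriptive statistics. No number of sites, annual caseload or precision argument accompanies either patient number.

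**The concern.** Both parts seek nearly the same patient in what reads as one collaboration. The prospective part also asks for consent and compliance, so on case definition alone it should collect cases no faster than a complete retrospective series. The stated numbers imply that it collects them seven times faster.

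This bears on two things. One is feasibility: if the long-run retrospective rate is the realistic one, the prospective cohort will be a handful of patients. The other is selection in the primary outcome: if the prospective rate is realistic, most past cases are absent from the retrospective series, and PLRS would describe whichever cases were retained. A descriptive analysis does not remove such selection. Section 7 names one mechanism by which it would arise, because the list starts from patients with stored tissue.

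**Working it through.** **Inputs.** Prospective: 50 patients in 36 months, or 3 years (Section 4.1). Retrospective: 100 patients (Section 5.1) from 1 January 1980 to 31 December 2021, or 42.0 years (Section 5). LR rate: 4% to 10% (Section 1). Neither target has a derivation in the Protocol, so neither can be reproduced. The check is whether they agree with each other.

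**Step 1: implied rates.**
- Retrospective: 100 / 42 = 2.38 per year.
- Prospective: 50 / 3 = 16.67 per year.
- Ratio: 16.67 / 2.38 = 7.0.

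**Step 2: each rate applied to the other window (assuming the same sites and steady incidence).**
- At 2.38 per year, 36 months give 3 × 2.38 = 7.1 patients, and 50 patients take 50 / 2.38 = 21 years.
- At 16.67 per year, 42 years give 16.67 × 42 = 700 cases, of which 100 is 14%. Put differently, 100 cases are 100 / 16.67 = 6 years of cases.

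**Step 3: can rounding explain it?** Both numbers are approximate. Suppose each is off by 20% in opposite directions (my assumption). The ratio then runs from (40/3) / (120/42) = 4.7 to (60/3) / (80/42) = 10.5. Rounding does not explain the gap.

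**Step 4: can growth in caseload explain it?** With exponential growth at log-rate g and complete capture, the 3 years after the 42-year window must hold half as many cases as the window itself: (e^(45g) − e^(42g)) / (e^(42g) − 1) = 50/100. The solution is growth of about 14% per year, sustained for 45 years.

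**Step 5: implied primary caseload at 4% to 10% LR.**
- Prospective: 16.67 / 0.10 = 167 to 16.67 / 0.04 = 417 treated patients per year.
- Retrospective: 2.38 / 0.10 = 24 to 2.38 / 0.04 = 60 per year.

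This is the same ratio on another scale, not independent evidence. It does give the sites a figure to compare with their own volumes.

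**Step 6: cost in precision of a prospective shortfall.** For a proportion of 50% without censoring (assumption), the approximate 95% half-width is 1.96 × √(0.25/n).
- Prospective cohort alone: 14 percentage points with n = 50, and 37 with n = 7.
- Both parts pooled: 8.0 points with n = 150, and 9.5 with n = 107.

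**Step 7: Section 5 against Section 7.** Section 5 claims every LR-first case. Section 7 starts from patients with tumour tissue. Following Section 7 as written gives a tissue-selected series, although the clinical outcome needs no tissue.

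**The case against.** The strongest reply is that the sevenfold ratio becomes a contradiction only under conditions the Protocol never states: the same sites in both parts, every site contributing for all 42 years, and constant incidence. No site count is given, and nothing says that each institution's database reaches back to 1980. The prospective intake may also be wider. Section 3 refers to all new cases coming to each site, which can include relapses first treated elsewhere, and Section 4.1 sets no limit on the LR date, so relapses before enrolment might count. The retrospective part has filters of its own (clinical information, and tissue under Section 7) that would hold 100 below full capture. All of this stands.

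A reader might therefore infer too much in four ways:
- **That the 36-month target cannot be met, or that one of the two numbers must be wrong.** Without site numbers and database start dates, the text does not force this.
- **That the prospective part would fail its objectives.** The objectives belong to the whole study, and no analysis is tied to the 50. A shortfall would reduce precision, modestly so in the pooled series.
- **That past cases are selected by which records survive.** The filters the text actually states are available clinical information and available tissue.
- **That 100 is a cap.** It is worded as an approximation.

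The reply does not remove the gap itself. None of these explanations is offered in the Protocol, and a sevenfold difference under claimed complete capture needs one. Nor does it reconcile Section 5 with Section 7; citing the tissue filter as a reason for the low number concedes that the series is not complete.

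**Conclusion.** The concern holds in a limited form. The two targets imply LR-first case rates of 2.4 and 16.7 per year for nearly the same definition in one collaboration, and the Protocol gives nothing to explain the factor of 7.0. The consequences (about 7 prospective patients instead of 50, or 100 cases out of about 700) rest on the same sites and steady incidence in both parts. They show the scale of the mismatch and are not predictions.

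The conflict between Section 5 and Section 7 needs no such assumption. The claim of complete capture and a list restricted to patients with tissue cannot both stand, and the restriction falls on the cohort that supplies most of the data for PLRS. Both the targets and the enrolment rule are fixed in the Protocol, so the matter should be settled there.

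**What to change.** 1. **Section 4.1:** name the sites, give their LR-first counts for the last few complete years, and restate the prospective number or the 36 months from that rate. State whether relapses before enrolment count.
2. **Section 5.1:** present the figure of about 100 as an estimate rather than a target, with the sites and the years behind it.
3. **Section 7:** remove the tissue condition for the clinical (PLRS) cohort and keep it for the optional sub-study only, so that the section agrees with Section 5.
4. **Sections 5 and 7:** have each site submit its full consecutive list of eligible cases for the period its database covers, and report listed against included cases by site, with reasons for omission.

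The cost is a database query at each site and revised wording. The stated prospective number may become less favourable. No additional patients are required for the correction itself.
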